# 2.2.1 Subgroup of interest

Exploratory analysis on the primary endpoint (Section 2.13.1) will be performed on following subset of FAS.

[figure not shown]
- FAS with baseline fibrosis stage of F2
- FAS with baseline fibrosis stage of F3
- FAS with T2DM at baseline
- FAS without T2DM at baseline
- FAS asian (Based on race collected on the Demographics CRF page)
- FAS non-asian (Based on race collected on the Demographic CRF page)

# 2.3 Patient disposition, demographics and other baseline characteristics

Demographics and baseline characteristics listed below will be summarized by study treatment on FAS.

- Age (years): per demographics CRF
- Age Group: two categories derived for age <65 years or age  $\ge 65$  years
- Gender: per demographics CRF
- Region: derived based on country of study site (Section 2.1)
- Ethnicity: per demographics CRF
- Race: per demographics CRF
- Height (cm) at screening visit
- Body Weight (kg)
- Waist circumference (cm)
- Hip circumference (cm)
- BMI

- Liver function (ALT, AST, ALP, GGT, TBL): see Section 2.1.1 for special baseline definition
- Steatosis stage (0, 1, 2 or 3) based on liver biopsy: categorical data summary
- Lobular inflammation stage (0, 1, 2 or 3) based on liver biopsy: categorical data summary
- Hepatocyte ballooning stage (0, 1 or 2) based on liver biopsy: categorical data summary
- NAS score (Section 5.3.8) based on liver biopsy: continuous data summary
- Fibrosis stage based on liver biopsy: categorical data summary for score 2 and 3
- Hepatic fat fraction based on MRI-PDFF
- Fasting lipids (HDL-C, LDL-C, VLDL-C, triglycerides, free glycerol, free fatty acid, total cholesterol, ApoA1)

Relevant medical histories up to baseline, including NASH specific co-morbidities, will be summarized by system organ class, preferred term and by study treatment on FAS.

#### 2.3.1 Patient disposition

The number of subjects in each analysis set will be presented overall for SCR and by study treatment (as randomized) for other analysis sets. Patients with the treatment received (Section 2.2 for SAF) different from the treatment group as randomized will be listed in the footnote.

The number (%) of subjects in RAN who completed the study, who withdraw from study early and the reason for early withdrawal will be presented by study treatment.

The number (%) of patients with protocol deviations and criteria leading to their exclusion from FAS and SAF will be presented for RAN.

# 2.4 Treatments (study treatment, rescue medication, concomitant therapies, compliance)

The analyses of treatments will use SAF.

# 2.4.1 Study treatment / compliance

The duration of exposure (days) to study treatment will be calculated as the LDDT – FDDT +1 and summarized by study treatment. In addition, the number (%) of patients with LDDT in the following time intervals after FDDT will be summarized by study treatment:

- <4 weeks
- $\geq 4$  and < 8 weeks
- $\geq 8$  and < 12 weeks
- $\geq$  12 and < 16 weeks
- $\geq 16$  and < 20 weeks
- $\geq 20$  and < 24 weeks
- $\geq$  24 and < 32 weeks
- $\geq$  32 and < 40 weeks
- $\ge 40$  and < 48 weeks
- $\geq$  48 weeks

The proportion of patients with dose reduction (including interruption) due to adverse event, as recorded in the change in dosing log CRF page, will be presented by study treatment.

Dose intensity is derived as the ratio between the cumulative dose of each active ingredient (tropifexor and licogliflozin) received during the study and duration of exposure (days). Patients in combination arm will have dose intensities derived separately for tropifexor and licogliflozin.

The relative dose intensity (compliance) is derived as the ratio between the actual dose intensity and the planned dose intensity which equals to the actual duration of exposure \* the daily dose of tropifexor or licogliflozin as planned according to protocol.

Number (%) of patients incompliant with planned regimen, defined as relative dose intensity >1.25 or <0.75, will be summarized for tropifexor in the LJN452 monotherapy arm, for licogliflozin in the LIK066 monotherapy arm, and for both tropifexor and licogliflozin separately in the combination arm.

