12.3 Treatments

The Safety set will be used for the analyses below. Categorical data will be summarized as frequencies and percentages. For continuous data, mean, standard deviation, median, 25th and 75th percentiles, minimum, and maximum will be presented.

The duration of exposure (days) to investigational treatment, the dose intensity (computed as the ratio of actual cumulative dose received and actual duration of exposure) and the relative dose intensity (computed as the ratio of dose intensity and planned dose intensity) will be summarized for the safety set. The proportion of participants with dose reduction will also be presented by treatment groups.

Proportion of participants non-compliance with the planned study treatment, which is defined as relative dose intensity >1.25 or <0.75, will be summarized descriptively for the double-blind treatment period.

Concomitant medications and significant non-drug therapies prior to and after the start of the study treatment will be listed and summarized by treatment group according to the World Health Organization (WHO), Anatomical Therapeutic Chemical (ATC) classification system.

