# 2.5 Analysis of the primary objective

The primary objective of the study is to demonstrate the efficacy of tropifexor + licogliflozin as assessed by histologic improvement after 48 weeks of combination treatment compared to each monotherapy treatment in patients with NASH and stage 2 or 3 fibrosis.

The following estimands framework is adopted to evaluate the objective.

- 1. Population: Full Analysis Set (FAS), for the adult population with NASH and stage 2 or 3 liver fibrosis as further defined with study inclusion and exclusion criteria.
- Variables of interest: histological response defined as resolution of NASH (absence of ballooning with no or minimal inflammation by histology) and no worsening of fibrosis OR improvement in fibrosis by at least one stage without worsening of NASH (worsening of hepatocellular ballooning or lobular inflammation) at week 48 compared with baseline. The criteria for changes in histologic endpoints are further detailed in Section 5.3.11.
- 3. Summary measure: odds ratio for the proportion of patients achieving histological response at week 48 between the combination and each monotherapy treatment.
- 4. Intercurrent events include
  - Early discontinuation of study treatment or withdrawal from study before week 48 visit.
  - Non-histologic clinical event suggesting treatment failures (e.g progression to cirrhosis, liver transplant and death due to disease).
  - Study treatment incompliance defined as relative dose intensity >1.25 or <0.75.
  - More than four weeks of accumulative exposure to any prohibited medications (Protocol Section 6.2.2), alcohol usage more than what is permitted in the protocol, initiation of other T2DM or lipid lowering medication (e.g. GLP-1 modulator), initiation of other treatment being evaluated or approved for NASH, or new concomitant interventions for weight control (e.g bariatric surgery) before the assessment for primary endpoint. The identification of relevant medications will be based on ATC3 and/or ATC5 codes, which will be included in analysis data set specifications. The list of concomitant interventions with significant effect for general weight loss will be determined based on blinded review of the study data.

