All practical measures will be exercised in the study to collect as much data as possible at week 48 despite intercurrent events (e.g. early discontinuation of study treatment). In the case of early withdrawal from the study on or after week 24, patient's histological response will be assessed if possible at the early termination visit.

A combination of the while-on-treatment and hypothetical strategies as defined in ICH E9 (R1) on handling intercurrent events will be adopted for the primary analysis.

If a patient discontinued study treatment early or withdrew early from the study without other inter-current event, but has histological response status collected after at least 24 weeks of study treatment, the primary endpoint will be imputed with their last histological response status

Novartis	For business use only	Page 20
SAP		CLJN452D12201C

assessed after at least 24 weeks of treatment. Patients with missing primary endpoint or primary endpoint after inter-current event(s) will have their primary endpoint data imputed with a multiple imputation (MI) method as outlined in Section 2.5.3 to estimate the treatment effect that would have been observed if all patients had continued on treatment for 48 weeks without intercurrent event.

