# 4 Change to protocol specified analyses

Analysis details, as well as editorial and semantic changes where appropriate, are implemented for different sections without altering the planned methods of analysis. The following significant changes from protocol are implemented in this SAP.

- 4.1 For the estimand definition in Section 2.5, one intercurrent event "Early discontinuation of study treatment or withdrawal from study before week 48 visit" is added to cover the two separately listed events "early stop of study treatment before week 24" and "premature study discontinuation before week 24" in original protocol. This updated intercurrent event also include the situation of early stop of study treatment or withdrawal from study after week 24 but before week 48. Such situation was implicitly considered as an intercurrent event, addressed with imputation but not explicitly listed as an intercurrent event in study protocol. This update does not change the primary analysis planned in the study protocol.
- 4.2 For the intercurrent events associated with prohibited medications, any alcohol usage more than what is permitted in the protocol, initiation of other T2DM or lipid lowering medication (e.g. GLP-1 modulator) or initiation of other treatment being evaluated or approved for NASH are also included as intercurrent event. This change is in consideration of newly identified interventions that may confound study treatment effect but not listed in the current version of study protocol.
- 4.3 Key secondary analyses are added into the hierarchical testing procedure after the primary analysis (Section 2.6). This change enables potentially more statistical evidence accumulation without affecting the primary analysis.
- 4.4 Formulation of the null and alternative hypotheses in Section 2.5 and 2.6 are updated based on odds ratio instead of difference as the test statistics. This update does not change the analysis method originally planned in protocol but to keep consistent with the actual test statistics that will be used for the hypothesis tests.
- 4.5 P-values will not be provided if formal hypothesis test is not performed. This change is implemented to avoid potential confusions or misinterpretation of the results.

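### Relative dose intensity in SAP 2.4.1 is wrong as written (1/duration at full adherence, not 1), and protocol v02 keeps the non-compliance event built on it without naming a strategy and with conflicting imputation text

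*SAP*

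**What the plan says.** **SAP.** Section 2.4.1 builds the measure in two steps. First, "Dose intensity is derived as the ratio between the cumulative dose of each active ingredient" and the days of exposure, worked out separately for tropifexor and licogliflozin in the combination arm. Second, relative dose intensity (RDI) is that quantity divided by "the planned dose intensity which equals to the actual duration of exposure" times the planned daily dose. Section 2.5 lists as an intercurrent event "Study treatment incompliance defined as relative dose intensity >1.25 or <0.75". It also says that patients with a missing endpoint or a "primary endpoint after inter-current event(s) will have their primary endpoint data imputed with a multiple imputation (MI) method". Section 2.5.3 repeats this. A patient who stops early and "has histological response status collected after at least 24 weeks of study treatment" keeps that result, but only if no other intercurrent event occurred.

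**Protocol v02.** Section 12.3 asks for "dose intensity (computed as the ratio of actual cumulative dose received and actual duration of exposure" and "relative dose intensity (computed as the ratio of dose intensity and planned dose intensity", and does not define the planned value further. Section 12.4 lists RDI outside 0.75 to 1.25 as an intercurrent event. Sections 2.1 and 12.4.3 give the same seven strategies: bariatric surgery, alcohol, confounding medication, premature discontinuation, death or transplantation, and liver conditions unrelated or related to treatment. Sections 12.4 and 12.8.1 reserve multiple imputation for data missing for reasons other than intercurrent events. Section 12.4.4, whose title confines it to that same kind of missingness, nevertheless imputes any primary endpoint that follows an intercurrent event.

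**The concern.** There are two linked defects.

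The SAP divides a rate (dose per day) by a total (dose over the whole exposure). The result is not a compliance ratio and cannot be compared with limits of 0.75 and 1.25. The flag it produces is an input to the primary estimand, so the text misstates whose biopsy counts as observed.

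Correcting the formula does not settle the matter in the current protocol. A participant with RDI of 0.70, say, has an intercurrent event under 12.4. The text allows three treatments of that participant's Week 48 biopsy: use it, impute it, or count non-response. If that choice is made after treatment codes are known, or made by a programmer without documentation, the primary analysis is no longer fully pre-specified for these participants.

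**Working it through.** **Inputs.** Planned treatment is 48 weeks (protocol 6.1.4), so 48 x 7 = 336 days. Daily doses are tropifexor 140 µg and licogliflozin 30 mg (protocol section 3). Exposure is last dose date minus first dose date plus 1 (SAP 2.4.1). The limits are 0.75 and 1.25. The documents give no worked RDI value, so there is no plan figure to reproduce.

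**Formula as written.** With duration D, daily dose q and cumulative dose C:

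RDI = (C / D) / (D x q)

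At full adherence C = D x q, so RDI = q / (D x q) = 1/D. The dose cancels, so the result is the same for both drugs.

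- Tropifexor, D = 336: 140 / (336 x 140) = 140 / 47,040 = 0.003
- Licogliflozin, D = 336: 30 / (336 x 30) = 30 / 10,080 = 0.003
- D = 168: 0.006; D = 28: 0.036; D = 2: 0.50; D = 1: 1.0

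A fully adherent patient is below 0.75 from the second day of exposure. To reach 0.75 at D = 336, the average intake would have to be 0.75 x 336 = 252 times the daily dose.

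**Formula as evidently intended.**

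RDI = C / (D x q)

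- Full adherence: 1.00 at any D.
- Lower limit at D = 336: 0.75 x 336 = 252. The flag means at most 251 doses taken, so 336 - 251 = 85 or more missed.
- Upper limit at D = 336: 1.25 x 336 = 420. The flag means more than 420 doses.

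**Protocol passages set side by side.**

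1. The events in 12.4 fall into four groups. Early discontinuation corresponds to item 4 of 12.4.3, clinical failure events to items 1 and 5, and alcohol and other medication to items 2 and 3. RDI non-compliance corresponds to none. Item 4 mentions adherence only as a reason for stopping treatment.
2. Items 2, 3 and 6 of 12.4.3, and item 4 for stopping after Week 24, use the observed biopsy despite the event. The clause in 12.4.4 would impute it. Both cannot hold.
3. Sections 12.4 and 12.8.1 confine imputation to missingness unrelated to intercurrent events. The clause in 12.4.4 extends it to observed values after such events.
4. RDI is computed from total dose and total exposure, so it has no date. For a participant who completes treatment it is known only at the last dose, about when the Week 48 biopsy is taken. One reading of after the event would then impute no completers; another would impute every flagged one.

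**An inconsistency that the open choice can produce.** A participant who stops just after Week 24 at full adherence has taken about 24 x 7 = 168 daily doses, and item 4 keeps the Week 48 biopsy. A participant who takes 251 of 336 doses has RDI 251/336 = 0.747, and 12.4.4 could impute that biopsy.

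**The case against.** The strongest reply is that nobody would implement the SAP formula literally. The measure is labelled compliance, its limits make sense only around 1, protocol 12.3 gives the ratio without the faulty denominator, and SAP section 4 lists no change to RDI, saying that details are "implemented for different sections without altering the planned methods of analysis". Duration times daily dose is the right denominator for cumulative dose; the slip is in calling it an intensity. All of that stands. It makes this a drafting error, and the practical risk is an undocumented correction.

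Three stronger readings are tempting and are not supported.

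- A reader might infer that the primary analysis would discard nearly all observed biopsies. That needs a literal reading of an evident slip and a settled meaning of after the event. It also needs the SAP's mix of while-on-treatment and hypothetical strategies, which protocol v02 replaced. The supportive analyses in SAP 2.5.4 do not use the flag.
- A reader might infer that the protocol has no rule at all for RDI non-compliance. Section 12.4.4 supplies imputation by default. The defect is that no strategy is named and that this default conflicts with other sections.
- A reader might infer that the SAP in force is out of date. The supplied SAP (09-Dec-2019) predates Amendments 01 and 02 and says it may be amended. The documents do not show whether a later one exists.

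The reply does not reach the conflict inside protocol v02, which does not depend on the age of the SAP.

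**Conclusion.** Wrong as written, and it should be fixed. The SAP formula gives 1/duration at full adherence (0.003 at 336 days) where it should give 1.00; this is exact algebra. Separately, protocol v02 retains the RDI event without a named strategy, and 12.4.4 contradicts 12.4, 12.4.3 and 12.8.1 on whether an endpoint observed after an intercurrent event is imputed.

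The effect on the treatment comparison cannot be sized from the documents. They give no expected share of participants outside 0.75 to 1.25 and no response rate for them, and the power calculation in 12.8.1 does not use RDI. The conclusion rests on the text of the supplied SAP and protocol v02, and on 336 days as full exposure for the dose counts.

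**What to change.** Before unblinding:

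1. **SAP 2.4.1.** Define RDI as cumulative dose taken divided by (duration of exposure x planned daily dose). State how the tropifexor and licogliflozin values in the combination arm form one flag. Define the measure for the placebo arm from the matching placebo units, since the supplied SAP defines it by active ingredient only and has no placebo arm.
2. **Protocol 2.1 and 12.4.3.** Name one strategy for RDI non-compliance. If the strategy depends on when the event occurs, define an onset.
3. **Protocol 12.4.4.** Delete the clause on endpoints after intercurrent events, or restrict it so that it agrees with 12.4, 12.4.3 and 12.8.1.

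The core SAP correction is one line, with short additions for the combination and placebo arms. Items 2 and 3 are a few sentences and may need a protocol amendment. No new data, visits or participants are needed.

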#### 2.4.2 **Prior and concomitant therapies**

Medications or other significant non-drug therapies during the study will be coded using the WHO dictionary.

Prior therapies are defined as any medications or significant non-drug therapies taken prior to the first administration of study treatment, regardless of whether stopped or continued after randomization.

Concomitant medications or non-drug therapies are defined as those received during the study treatment and follow-up periods (i.e., until end of study visit) regardless of whether started before randomization. Therefore, a medication can be BOTH prior and concomitant.

Number (%) of patients using prior and concomitant medications will be summarized separately by the 3rd and 5th level ATC terms and by study treatment on FAS.

# 2.5 Analysis of the primary objective

The primary objective of the study is to demonstrate the efficacy of tropifexor + licogliflozin as assessed by histologic improvement after 48 weeks of combination treatment compared to each monotherapy treatment in patients with NASH and stage 2 or 3 fibrosis.

The following estimands framework is adopted to evaluate the objective.

- 1. Population: Full Analysis Set (FAS), for the adult population with NASH and stage 2 or 3 liver fibrosis as further defined with study inclusion and exclusion criteria.
- Variables of interest: histological response defined as resolution of NASH (absence of ballooning with no or minimal inflammation by histology) and no worsening of fibrosis OR improvement in fibrosis by at least one stage without worsening of NASH (worsening of hepatocellular ballooning or lobular inflammation) at week 48 compared with baseline. The criteria for changes in histologic endpoints are further detailed in Section 5.3.11.
- 3. Summary measure: odds ratio for the proportion of patients achieving histological response at week 48 between the combination and each monotherapy treatment.
- 4. Intercurrent events include
  - Early discontinuation of study treatment or withdrawal from study before week 48 visit.
  - Non-histologic clinical event suggesting treatment failures (e.g progression to cirrhosis, liver transplant and death due to disease).
  - Study treatment incompliance defined as relative dose intensity >1.25 or <0.75.
  - More than four weeks of accumulative exposure to any prohibited medications (Protocol Section 6.2.2), alcohol usage more than what is permitted in the protocol, initiation of other T2DM or lipid lowering medication (e.g. GLP-1 modulator), initiation of other treatment being evaluated or approved for NASH, or new concomitant interventions for weight control (e.g bariatric surgery) before the assessment for primary endpoint. The identification of relevant medications will be based on ATC3 and/or ATC5 codes, which will be included in analysis data set specifications. The list of concomitant interventions with significant effect for general weight loss will be determined based on blinded review of the study data.

All practical measures will be exercised in the study to collect as much data as possible at week 48 despite intercurrent events (e.g. early discontinuation of study treatment). In the case of early withdrawal from the study on or after week 24, patient's histological response will be assessed if possible at the early termination visit.

A combination of the while-on-treatment and hypothetical strategies as defined in ICH E9 (R1) on handling intercurrent events will be adopted for the primary analysis.

If a patient discontinued study treatment early or withdrew early from the study without other inter-current event, but has histological response status collected after at least 24 weeks of study treatment, the primary endpoint will be imputed with their last histological response status

Novartis	For business use only	Page 20
SAP		CLJN452D12201C

assessed after at least 24 weeks of treatment. Patients with missing primary endpoint or primary endpoint after inter-current event(s) will have their primary endpoint data imputed with a multiple imputation (MI) method as outlined in Section 2.5.3 to estimate the treatment effect that would have been observed if all patients had continued on treatment for 48 weeks without intercurrent event.

